8.2.3.1 Efficacy Endpoints

Primary Efficacy Endpoint

- Average TCS during the peak RS.

Key Secondary Efficacy Endpoints

- Average TCS during the entire RS;
- Average rhinoconjunctivitis DSS during the peak RS;
- Average rhinoconjunctivitis DMS during the peak RS.

Tertiary Efficacy/Immunologic Endpoints

- Average rhinoconjunctivitis DSS during the entire RS
- Change from baseline in IgE level against *Ambrosia artemisiifolia* at Visit 6 and at Visit 8;
- Change from baseline in IgG₄ level against *Ambrosia artemisiifolia* at Visit 6 and at Visit 8.

Exploratory Efficacy Endpoints

- Average Asthma DSS during the peak RS and the entire RS; Average daily number of puffs of as-needed SABA used during the peak RS and the entire RS;

- Average weekly number of nights with nocturnal awakening due to asthma symptoms requiring SABA use during the peak RS and the entire RS.

8.2.3.2 Safety Endpoints

Tier 1 Safety Endpoints

- Proportion of subjects reporting pre-specified local application site reactions (including adverse events related to lip swelling/edema, mouth swelling/edema, palatal swelling/edema, swollen tongue/edema, oropharyngeal swelling/edema, pharyngeal edema/throat tightness, oral pruritus, throat irritation, tongue pruritus, and ear pruritus);
- Proportion of subjects reporting anaphylaxis and/or systemic allergic reactions;
- Proportion of subjects treated with epinephrine.

Tier 2 Safety Endpoints

- Proportion of subjects with any AE;
- Proportion of subjects with any serious AE;
- Proportion of subjects with any drug-related AE;
- Proportion of subjects with any serious and drug-related AE;
- Proportion of subjects who discontinue due to an AE;
- Proportion of subjects with specific AEs or SOCs (incidence \geq 1% subjects in one or more of the treatment groups).

Tier 3 Safety Endpoints

- Change from baseline in laboratory test parameters at each post-baseline visit;
- Change from baseline in vital sign parameters at each post-baseline visit;
- Summaries by system organ class (SOC) for general AEs, serious AEs, drug-related AEs, and AEs resulting in discontinuation;
- Average duration of pre-specified local application site reactions in minutes on Day 1;
- Average duration of pre-specified local application site reactions in days over Day 2 to Day 14;
- Average duration of pre-specified local application site reactions in days over Day 15 to Day 28.

8.2.3.3 Derivations of Efficacy/Immunologic Endpoints

Ragweed Season

Entire Ragweed Season: the start of the entire ragweed season is the first day of 3 consecutive recorded days with a pollen count of ≥ 10 grains/m³; the end of the entire ragweed season is the last day of 3 consecutive recorded days with a pollen count of ≥ 10 grains/m³. This is specific for each study site.

Peak ragweed season: the 15 consecutive recorded days within the entire ragweed season with the highest 15-day moving average pollen count. This is specific for each study site.

TCS, Rhinoconjunctivitis DSS, Rhinoconjunctivitis DMS, Asthma DSS

These are defined in Section 4.2.3.1.

8.2.3.4 Derivations of Safety Endpoints

For laboratory tests and vital sign parameters, the baseline value is defined as the last measurement taken prior to randomization. Change from baseline in laboratory and vital signs parameters is calculated by on-treatment value minus the baseline value.

8.2.4 Analysis Populations

8.2.4.1 Efficacy Analysis Populations

The Full Analysis Set (FAS) population will serve as the primary population for the analysis of efficacy data in this study. The FAS population consists of all randomized subjects who receive at least one dose of study treatment. Subjects will be analyzed according to the treatment group to which they are randomized.

A supportive analysis using the Per-Protocol (PP) population will be performed for the primary efficacy endpoint. The PP population excludes subjects due to important deviations from the protocol that may substantially affect the results of the primary efficacy endpoints. The major protocol violations that would lead to exclusion of a subject or a data point are described below:

- Subjects with asthma requiring prescribed high daily doses of inhaled corticosteroids (as defined in the protocol);
- Subjects with chronic sinusitis during the previous 2 years;
- Subjects treated with immunotherapy within 5 years prior to screening;
- Subjects unable to meet medication washout requirements;
- Subjects randomized in the study more than once;
- Subjects who participated in the same study at another site;
- Subjects with pre-seasonal duration of treatment exposure < 56 Days;
- Subjects with a negative skin prick test response to ragweed;
- Subjects with specific IgE to ragweed < 0.7 kU/L;

- Subjects with overall treatment compliance < 75% between Visit 2 and Visit 8;
- Subjects who took prohibited medications as defined in the protocol, with the exception of antihistamines. Subjects who have taken antihistamines (other than sponsor provided rescue medications) will be considered protocol violators if they have taken the medication for 2 or more consecutive days between Visit 6 and Visit 8;
- Subjects who had their blinded treatment randomization code broken.

Analyses related to SABA use and nocturnal awakening will be based on subjects with asthma in the FAS population.

8.2.4.2 Safety Analysis Populations

The All-Subjects-as-Treated (ASaT) population will be used for the analysis of safety data in this study. The ASaT population consists of all randomized subjects who received at least one dose of study treatment. Subjects will be grouped by the study treatment actually received.

8.2.5 Statistical Methods

Statistical testing and inference for efficacy and safety analyses are described in Sections 8.2.5.1 and 8.2.5.2. Controlling of family-wise Type I error rate is described in Section 8.2.6, Multiplicity. Nominal p-values will be computed for tertiary and exploratory efficacy analyses as a measure of strength of association between the endpoint and the treatment effect rather than formal tests of hypotheses. Unless otherwise stated, all statistical tests will be conducted at $\alpha=0.05$ (2-sided) level.

8.2.5.1 Statistical Methods for Efficacy/Immunologic Analyses

Primary Efficacy Analysis

The primary efficacy endpoint for the current trial is the average TCS during the peak ragweed season. It will be analyzed using the ANOVA model, which includes fixed effects of treatment, baseline asthma status (yes, no), age group (5 to 11 years, 12 to 17 years), pollen season, and pollen region nested within pollen season. Pollen region will be defined based on pollen station, and may include several sites within an acceptable distance between the pollen counters and corresponding sites.

Two-sided 95% CI of the treatment difference in adjusted means will be presented. Also, the treatment difference in adjusted means relative to the adjusted mean of the placebo group will be presented as a percentage with corresponding 2-sided 95% CI derived using the bootstrap method. No missing data will be imputed.

The normality assumption of the ANOVA model will be checked using the Shapiro-Wilk test and inspection of the Q-Q plot. If a severe violation is observed, the primary analysis will be based on Wilcoxon Rank Sum test; the p-value will be reported together with the associated Hodges-Lehmann estimate of the treatment difference and its 2-sided 95% CI. Also, the difference in the treatment group medians relative to the median of the placebo group will be

presented as a percentage with the corresponding 2-sided 95% CI derived using the bootstrap method.

Sensitivity Analysis

The PP analysis will be conducted for the primary efficacy endpoint, where the same ANOVA model and missing data approach will be used. In addition, the following sensitivity analyses will be performed for the primary efficacy endpoint.

- The same ANOVA model based on the FAS population will be used. Missing data will be imputed by the LOCF approach. For each subject, only the observations within the pollen season are eligible to be carried forward.
- The same ANOVA model based on the FAS population will be used. Missing data will be handled by the multiple imputation method. Missing data from both treatment groups will be imputed using the sample distribution of TCS observed from the placebo group, which is considered to be a conservative approach for imputations.
- Longitudinal Data Analysis model based on the FAS population will be used. Daily TCS during the peak season will be the response variable and covariates will include treatment, time, the interaction of treatment by time, baseline asthma status, age group, pollen season, and pollen region nested within pollen season. The Toeplitz structure will be used to model the covariance of the repeated TCS measurements over time within subjects. Additional covariance structures, such as unstructured covariance, may be considered if convergence issues are encountered with the analysis model.

Furthermore, if there are more than 2% of subjects taking prednisone during any one ragweed season in the course of the study, a sensitivity analysis will be conducted for the primary efficacy endpoint, where the usage of prednisone is included in the definition of the rhinoconjunctivitis DMS. The medication scores for prednisone usage are defined in [Table 9](#).

Table 9 Medication Score for Prednisone Usage

Rescue Medication	Subject Dosing Instructions	Score/Dose Unit	Maximum Daily Score
Prednisone tablet 5 mg	Day 1: 1 mg/kg/day, Max 50 mg/day	1.6 (per tablet)	16
	Day 2+: 0.5 mg/kg/day, Max 25 mg/day	1.6 x 2 (per tablet)	16

In addition, in order to minimize missing data, subjects will be allowed to complete the daily e-diary up to 9 am the following morning (in case the subject cannot complete it at their regular time that day). A sensitivity analysis will be conducted for the FAS population, where only the data entered on the same day (instead of next morning) are included. The same ANOVA model and missing data approach will be used.

Key Secondary Efficacy Analyses

The key secondary efficacy endpoints for the current trial include:

- Average TCS during the entire RS;
- Average rhinoconjunctivitis DSS during the peak RS;
- Average rhinoconjunctivitis DMS during the peak RS.

These endpoints will be analyzed based on the FAS population using the same ANOVA model as the primary efficacy endpoint.

Based on the rescue medication usage from previous AIT trials, many subjects used little rescue medication during the trial, which resulted in large amounts of rhinoconjunctivitis DMS records equal to zero. Data with excessive zeroes may not conform to the normality assumption for the ANOVA model and may also prevent the proper application of non-parametric method. In a situation when there are more than 30% of the daily rhinoconjunctivitis DMS equal to zero, the zero-inflated lognormal model [18] will be used as the primary analysis method for rhinoconjunctivitis DMS as appropriate; this model takes the average rhinoconjunctivitis DMS during the peak RS as response and adjusts for the same terms as in the ANOVA model.

Tertiary Efficacy/Immunologic Analyses

The tertiary efficacy/immunologic endpoints for the current trial include:

- Average rhinoconjunctivitis DSS during the entire RS;
- Change from baseline in IgE level against *Ambrosia artemisiifolia* at Visit 6;
- Change from baseline in IgE level against *Ambrosia artemisiifolia* at Visit 8;
- Change from baseline in IgG₄ level against *Ambrosia artemisiifolia* at Visit 6;
- Change from baseline in IgG₄ level against *Ambrosia artemisiifolia* at Visit 8.

Average rhinoconjunctivitis DSS during the entire RS will be analyzed based on the FAS population using the same ANOVA model as the primary efficacy endpoint.

IgE and IgG₄ related endpoints will be analyzed separately using the constrained LDA (cLDA) model. The cLDA model assumes a common mean across treatment groups at baseline and different means for different treatments at each post-baseline time point. In this model, the response vector consists of the baseline value and the values observed at each post-baseline time point. The model will adjust for time, the interaction of treatment by time, baseline asthma status, age group, pollen season, and pollen region nested within pollen season. Time is treated as a categorical variable so that no restriction is imposed on the trajectory of the means over time. A Toeplitz covariance matrix will be used to model the correlation among repeated measurements. Further details of the model specification, assumptions, and SAS implementation codes will be provided in the sSAP.

Exploratory Efficacy Analyses

The exploratory efficacy endpoints for the current trial include:

- Average Asthma DSS during the peak RS;
- Average Asthma DSS during the entire RS;
- Average daily number of puffs of as-needed SABA used during the peak RS;
- Average daily number of puffs of as-needed SABA used during the entire RS;
- Average weekly number of nights with nocturnal awakening due to asthma symptoms requiring SABA use during the peak RS;
- Average weekly number of nights with nocturnal awakening due to asthma symptoms requiring SABA use during the entire RS.

These endpoints will be analyzed using the same ANOVA model as the primary efficacy endpoint. Asthma DSS related endpoints will be analyzed based on the FAS population, while SABA use and nocturnal awakening related endpoints will be analyzed based on subjects with asthma in the FAS population.

In addition, components of the rhinoconjunctivitis DSS (ocular symptoms and nasal symptoms) will be summarized for the peak RS and the entire RS.

Table 10 summarizes the key analysis strategy for the efficacy/immunologic endpoints.

Table 10 Analysis Strategy for the Efficacy/Immunologic Endpoints

Endpoint	Statistical Method ^a	Analysis Population	Missing Data Approach
Primary Efficacy Endpoint			
Average TCS during the peak RS	ANOVA	FAS	Observed data only
			LOCF
		PP	Multiple Imputation ^b
			Observed data only
	Wilcoxon Rank Sum Test; Hodges-Lehmann estimate of treatment difference ^c	FAS	Observed data only
	Longitudinal Data Analysis	FAS	Model based
Key Secondary Efficacy Endpoints			
Average TCS during the entire RS	ANOVA	FAS	Observed data only
Average rhinoconjunctivitis DSS during the peak RS	ANOVA	FAS	
Average rhinoconjunctivitis DMS during the peak RS	ANOVA	FAS	
	Zero-inflated log-normal ^c		
Tertiary Efficacy/Immunologic Analyses			
Average rhinoconjunctivitis DSS during the entire RS	ANOVA	FAS	Observed data only
Change from baseline in IgE level against Ambrosia artemisiifolia at Visit 6 and Visit 8	constrained Longitudinal Data Analysis	FAS	Model based

Endpoint	Statistical Method ^a	Analysis Population	Missing Data Approach
Change from baseline in IgG ₄ level against Ambrosia artemisiifolia at Visit 6 and Visit 8	constrained Longitudinal Data Analysis	FAS	Model based
Exploratory Efficacy Analyses			
Average Asthma DSS during the peak RS and the entire RS	ANOVA	FAS	Observed data only
Average daily number of puffs of as-needed SABA used during the peak RS and the entire RS	ANOVA	FAS (asthma only)	Observed data only
Average weekly number of nights with nocturnal awakening due to asthma symptoms requiring SABA use during the peak RS and the entire RS	ANOVA	FAS (asthma only)	Observed data only

ANOVA = Analysis of Variance; DSS = Daily Symptom Score; DMS = Daily Medication Score; FAS = Full Analysis set; IgE = immunoglobulin E; IgG₄ = immunoglobulin G₄; LOCF = Last non-missing observation carried forward; PP = Per Protocol; RS = Ragweed Season; SABA = short-acting beta₂-agonist; TCS = Total Combined Score.

^a Details of the statistical models are described in Section 8.2.5.

^b Missing data from both treatment groups will be imputed using the sample distribution of TCS observed from the placebo group.

^c This method will be applied if excessive zeros are observed in the data.

Handling of Missing Data

The missing data approaches are specified for the primary efficacy endpoint sensitivity analyses (including multiple imputation, LOCF, and model based) and immunologic endpoints (model based). All other analyses will be conducted based on the observed data only. Proportion of subjects with missing data will be summarized for each efficacy/immunologic endpoint.

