1. Have a legal representative who provides written informed consent for the trial on the subject's behalf after understanding the study procedures, alternative treatments available, risks involved with the study, and voluntarily agreeing to allow the subject to participate. The legal representative may also provide consent for Future Biomedical Research on the subject's behalf. However, the subject may participate in the main trial without participating in Future Biomedical Research. The subject, depending on their age and ability to understand the nature and intent of the study, must also assent to participate in the study main trial and to Future Biomedical Research.

2. Be ≥ 4 to ≤ 17 years of age on the day informed consent is obtained from the legal representative, however, the subject must be ≥ 5 years old at the Randomization Visit. The subject may be of either gender and any race/ethnicity.
3. Have a clinical history of significant ragweed pollen-induced allergic rhinitis/rhinoconjunctivitis of ≥ 1 year (at least 1 season for ages 4 to 6 years) or ≥ 2 years (at least 2 seasons for ages 7 to 17 years) duration diagnosed by a physician (with or without asthma) and have received treatment for the condition during the previous ragweed season.

Note: If medical records are not available, verbal history from subject/parent/legal guardian may be elicited at the Screening Visit and can be used to fulfill this criterion if documented in the subject study file by the investigator.

4. Have a positive skin prick test response (average wheal diameter ≥ 5 mm larger than the saline control after 15 to 20 minutes) to *Ambrosia artemisiifolia* at the Screening Visit.

Note: The test can have been performed up to 1 year before the Screening Visit if the skin prick test reagents and prick devices used are the same as provided for this trial.

5. Have a specific IgE against *Ambrosia artemisiifolia* \geq IgE Class 2 (0.7 kU/L) at the Screening Visit.
6. Have a forced expiratory volume in 1 second (FEV₁) $\geq 80\%$ of predicted value at the Screening and Randomization Visits (following at least a 6-hour washout of short-acting beta₂-agonists, 12-hour washout of twice daily long-acting beta₂-agonists, or 24-hour washout of once daily long-acting beta₂-agonists).

Note: Long-acting inhaled beta₂-agonists are prohibited within 30 days prior to randomization and for the duration of the study.

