7.1.3.1 Serum-specific IgE

Blood samples will be collected at screening (Visit 1) for determination of serum-specific IgE against ragweed (*Ambrosia artemisiifolia*), other weeds (dependent upon region), grasses (dependent upon region), oak and other trees (dependent upon region), cat, dog, alternaira, cladosporium, dust mites, mugwort, and other allergens considered clinically relevant for a particular locale.

A subject must have a specific IgE against *Ambrosia artemisiifolia* of ≥ 0.7 kU/L at screening to be included in the trial.

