8.2.5.3 Summaries of Baseline Characteristics, Demographics, and Other Analyses

Demographic and Baseline Characteristics

The number and percentage of subjects screened, randomized, the primary reasons for screening failure, and the primary reason for discontinuation will be displayed.

Demographic variables (including age, gender, race, weight, height, and body mass index), baseline characteristics (including baseline asthma status, inhaled corticosteroid use, duration of allergic rhinitis, sensitization type, ragweed specific IgE, wheal size from skin prick test, and number of puffs of bronchodilator used for FEV₁ reversibility), primary and secondary diagnoses, and prior and concomitant therapies will be summarized by treatment either by descriptive statistics or categorical tables. The comparability of the treatment groups for each relevant characteristic will be assessed by the summary tables. No statistical hypothesis tests will be performed on these characteristics.

Skin Prick Test (SPT) Analysis

Descriptive statistics (mean, standard deviation, etc.) of the wheal size determined from the SPT will be provided for all randomized subjects.

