##### **3.2.5.1 Statistical Methods for Efficacy/Immunologic Analyses**

###### **Primary Efficacy Analysis**

The primary efficacy endpoint for the current trial is the average TCS during the peak ragweed season. It will be analyzed using the ANOVA model, which includes fixed effects of treatment, baseline asthma status (yes, no), age group (5 to 11 years, 12 to 17 years), pollen season, and pollen region nested within pollen season. Pollen region will be defined based on pollen station and may include several sites within an acceptable distance between the pollen counters and corresponding sites.

Two-sided 95% CI of the treatment difference in adjusted means will be presented. Also, the treatment difference in adjusted means relative to the adjusted mean of the placebo group will be presented as a percentage with corresponding 2-sided 95% CI derived using the bootstrap method. No missing data will be imputed.

The normality assumption of the ANOVA model will be checked using the Shapiro-Wilk test and inspection of the Q-Q plot. If a severe violation is observed, the primary analysis will be based on Wilcoxon Rank Sum test; the p-value will be reported together with the associated Hodges-Lehmann estimate of the treatment difference and its 2-sided 95% CI. Also, the difference in the treatment group medians relative to the median of the placebo group will be presented as a percentage with the corresponding 2-sided 95% CI derived using the bootstrap method.

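### The primary ANOVA may forgo some precision by leaving out ragweed-specific IgE and skin-prick wheal size, both known before randomisation

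*Protocol*

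**What the plan says.** Protocol 8.2.5.1 specifies an ANOVA "which includes fixed effects of treatment, baseline asthma status (yes, no), age group (5 to 11 years, 12 to 17 years), pollen season", plus a term for region within season. Sections 3.1.1 and 3.2.5.1 of the supplemental SAP repeat these terms, ending with "pollen season, and pollen region nested within pollen season". Section 3.1.1 also sets region to country, with the United States split in two. Age group and asthma status are the two randomisation strata (Protocol 5.4). The key secondary endpoints use the same model, and the zero-inflated lognormal model for the medication score (DMS) uses the same terms.

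Both omitted variables are inclusion criteria in Protocol 5.1.2. The IgE criterion requires at least "IgE Class 2 (0.7 kU/L) at the Screening Visit". The skin-test criterion begins "Have a positive skin prick test response (average wheal diameter" and requires a wheal at least 5 mm above saline. Its note says "The test can have been performed up to 1 year before the Screening Visit" if the reagents and devices are the same as the trial's. Protocol 7.1.3.1 confirms the timing for IgE: "Blood samples will be collected at screening (Visit 1) for determination of serum-specific IgE against ragweed".

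Apart from eligibility and the matching per-protocol exclusions (Protocol 8.2.4.1), the two variables appear only among the characteristics to be summarised: "ragweed specific IgE, wheal size from skin prick test" (Protocol 8.2.5.3; supplemental SAP 3.2.6). Neither document says why they are not covariates.

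**The concern.** A symptom-score trial would usually adjust for the baseline score. This one cannot. The e-diary is issued at Visit 4 and its medication section opens at Visit 6 (Protocol 6.0), both after randomisation and several weeks of treatment. The only subject-level terms in the model are therefore two binary factors.

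If degree of sensitisation predicts seasonal TCS beyond the planned terms, adjusting for it would shrink the residual variance and narrow the confidence interval. It would also remove the effect of any chance imbalance in sensitisation. The precision matters most for the target on which the trial was sized, an upper confidence limit below -10%, which has only about 90% power. The three key secondary endpoints have no stated power and would carry the same terms.

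**Working it through.** **Inputs.** From Protocol 8.2.7 (repeated in supplemental SAP 3.2.8): true difference -2.12, placebo mean 8.9, SD 5.60, 1000 subjects randomised 1:1, 15% dropout. From Protocol 8.2.5: "all statistical tests will be conducted at" two-sided 0.05, so the critical value is 1.96. The correlation of IgE and wheal size with TCS is not given and is assumed.

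**The plan's own figure.** Evaluable subjects per arm: 500 × 0.85 = 425. The assumed relative difference is -2.12/8.9 = -23.8%. The margin beyond -10% is 2.12 - 0.10 × 8.9 = 1.23.

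- Placebo mean taken as fixed: SE = 5.60 × √(2/425) = 0.384. Power = Φ(1.23/0.384 - 1.96) = 89.3%, which reproduces the stated figure of about 90%.
- Sampling error in the placebo mean allowed for (testing active mean minus 0.9 × placebo mean): SE = 5.60 × √(1.81/425) = 0.365. Power = Φ(1.23/0.365 - 1.96) = 92.0%.
- Test of zero difference: Φ(2.12/0.384 - 1.96) = 99.98%.

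The plan takes its interval for the relative difference from a bootstrap, so the first two lines are approximations to it.

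**Effect of adjustment.** Let r be the multiple correlation of the two covariates with TCS beyond the planned terms, and take 5.60 as the residual SD under those terms. The SD becomes 5.60 × √(1 - r²). The interval for the treatment difference narrows by 1 - √(1 - r²), and the equivalent sample size is 425/(1 - r²) per arm.

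| r | Residual variance falls | Interval narrower | Equivalent n per arm | Power for -10%, placebo mean fixed | Power for -10%, placebo error included |
|---|---|---|---|---|---|
| 0 | 0% | 0% | 425 | 89.3% | 92.0% |
| 0.1 | 1% | 0.5% | 429 | 89.6% | 92.3% |
| 0.2 | 4% | 2.0% | 443 | 90.5% | 93.0% |
| 0.3 | 9% | 4.6% | 467 | 91.9% | 94.2% |
| 0.4 | 16% | 8.3% | 506 | 93.7% | 95.7% |

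Power against zero difference is at least 99.98% in every row.

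**Cost.** With 850 evaluable subjects and, for illustration, 20 parameters already in the model, two more multiply the SE by about √(830/828) = 1.0012 if the covariates explain nothing. That is about 0.1%.

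**The case against.** The strongest reply is that there is no error here. The model contains both stratification factors and the exposure terms, a randomised comparison is unbiased without further covariates, and the stated power reproduces without them. The primary hypothesis and the fixed testing sequence turn on significance against zero, where power is already about 99.98%. All of this stands.

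A reader might infer from the omission that precision is certainly being lost. The documents do not support that. They give no correlation, and at r = 0.1 the gain is only 0.3 points of power. The entry floors may restrict the range of both variables and weaken any association. The gain also depends less on the plan than on the approximation chosen: different formulas for the relative difference give a starting power of 89.3%, 92.0% or 95.0% (the last by the delta method on the ratio). That spread is wider than the gain across the whole assumed range.

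Two practical limits also stand. If normality is severely violated, the primary analysis becomes a Wilcoxon rank sum test, which has no covariates as written. And the wheal need not come from screening: the qualifying test may be up to a year older, and screening itself may last about 12 months, so a wheal could be about two years old at randomisation.

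The reply does not show that adjustment would do harm. Both variables are fixed before randomisation, should be nearly complete because eligibility depends on them, and cost almost nothing to include.

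**Conclusion.** The point holds as an optional gain in efficiency. The primary ANOVA may forgo some precision, and how much cannot be determined from the documents. For an assumed multiple correlation of 0 to 0.4, the gain in power for the -10% target runs from nothing to 4.4 points (89.3% to 93.7%) or 3.7 points (92.0% to 95.7%), depending on how the placebo mean is treated. This rests on the plan's own mean, difference and SD, on reading 5.60 as the residual SD, and on the ANOVA being retained.

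It would be wrong to conclude that the treatment estimate is biased, that the trial is too small or that its stated power is wrong. The check contradicts the last of these and nothing in the documents supports the other two. No figure can be given for the key secondary endpoints, because the plan states no assumptions for them.

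**What to change.** Before unblinding, amend the protocol to add two continuous covariates to the ANOVA for the primary and key secondary endpoints:

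- log ragweed-specific IgE from the screening visit;
- mean ragweed wheal diameter net of saline, from the qualifying skin prick test before randomisation, stating that this test may precede screening by up to 1 year.

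Add the same two terms to the zero-inflated lognormal model for DMS, so that it keeps the ANOVA's terms. Fix their form in the amendment, and say how a missing covariate value is handled so that no subject drops out of the full analysis set. State that the covariates have no role under the Wilcoxon fallback. Do not use diary scores from Visit 4 onward as a baseline, because they are recorded on treatment.

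The cost is the amendment, which Protocol 8.2 requires for a change to the primary or key secondary methods, and two degrees of freedom. No new data, visits or procedures are needed.
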